**Additional Study Investigators:**

[name]  
[name], M.Sc.  
[name] [name]  
[name]  
[name]  
[name] Sc.M.  
[name]  
[name]  
[name], MS

**1. Abstract** (Provide no more than a one page research abstract briefly stating the problem, the research hypothesis, and the importance of the research)

Within the last decade, Linac based stereotactic body radiation therapy (SBRT) has been shown to be an effective treatment option for pancreas and liver tumors. SBRT delivers high doses of radiation therapy to the tumor over only 1-5 treatments. Because of the spatial precision of SBRT, it is feasible to administer a high radiation dose in only a few treatments. By minimizing the amount of radiation to surrounding healthy tissue, it is possible to decrease the rate of toxicity/complication and increase the radiation dose to cancerous tissue, thereby allowing better local control.

SBRT of the abdomen has been limited by the movement of intra-abdominal organs that naturally occurs with respiration and bowel movement. Organ motion occurs both intra- and interfractionally.

While intrafractional motion is a result of respiration, peristalsis and cardiac motion, the magnitude of interfractional target motion is dependent of daily variations in organ filling, weight change, tumor growth and radiation induced changes of tissue. Tumor movement may lead to tumor displacement and suboptimal dose delivery. Accurate localization of the target is very important to improve treatment delivery accuracy and reduce toxicity of the treatment. To evaluate tumor motion due to breathing motion, a 4-D CT simulation scan is performed. If the tumor moves more than 3 mm during a breathing cycle, breathing motion management is employed using Active Breathing Control (ABC) technique. ABC requires the patient to hold his/her breath within the proper tidal volume while treatment is delivered, while free breathing may be resumed between periods of treatment. This technique limits the delivery of RT to specific phases of the respiratory cycle so as to minimize the influence of breathing on the delineated tumor.

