Despite significant progress made in ABC technique, tumor and organ motion could only be minimized and not eliminated completely. Assessing patient specific tumor/organ motion (both intra- and interfractional) throughout the course of SBRT treatment offers the possibility of ensuring delivery of the prescribed target dose while simultaneously minimizing normal tissue damage. In order to monitor the abdominal soft tissue motion, the Department of Radiation Oncology has developed a 4D ultrasound technique based on an ultrasound probe holder and a continuous motion monitoring software.

The 4D ultrasound image is acquired by using a motorized 3D ultrasound probe and image continuously. 4D ultrasound is a new non-ionizing and non-invasive imaging technique that allows continuous image acquisitions for real-time motion monitoring during the radiation treatment. Ultrasound is a proven modality for soft tissue localization (ref-prostate-breast). Several studies  have shown that even with older version of ultrasound system, the ultrasound images correlates with CT images within a small absolute magnitude of difference (about 3 mm), therefore we expect to have good agreement between the reference CT simulation and reference 4D ultrasound. Ultrasound motion monitoring during treatment delivery is based on real-time automatic registration of ultrasound images acquired on treatment days to reference ultrasound images acquired at the beginning of treatment, thus removing any inter-modality tracking uncertainty and inter-user variability. The ultrasound probe in the CT image will be contoured and radiation beams that directly pass through the ultrasound probe will be avoided. An SBRT treatment plan usually consist of multiple (9 – 12 beams for IMRT technique) co-planar beams delivered around the isocenter placed inside the tumor. Omitting the small range of angle directly passing through the ultrasound probe will not compromise the treatment plan dosimetry quality.

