## **2. Objectives** (include all primary and secondary objectives)

### Primary objectives:

- a. Establish effective workflow for real time monitoring of abdominal soft-tissue motion due to respiration using 4D ultrasound system
- b. Evaluate feasibility of real time motion monitoring of tumor and surrounding organ/tissue during pancreas and liver SBRT treatments using 4D ultrasound system
- c. Evaluate accuracy of the 4D ultrasound motion monitoring system compare to CBCT based intra-fraction motion monitoring during pancreas and liver SBRT treatments

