On each treatment day, 4D ultrasound images will be acquired continuously during beam on time to monitor pancreas motion. The system will record all relevant images, but will not be used in clinical decision making. These data will be used to evaluate the magnitude of target motion and dosimetry deviation due to the motion. Intra-fraction CBCT images acquired during treatment will be registered with reference CT images. Organ motion registered by ultrasound will be compared to motion recorded by CBCT and the accuracy of the ultrasound system will be evaluated.

c. **Arm 3:** Monitor the abdominal soft tissue motion of liver patients receiving SBRT treatment with ABC during the whole course of treatment.

Twenty hepatic cancer patients being treated with SBRT treatment will be enrolled and informed consent obtained per study guidelines as described. A 4D ultrasound scan will be acquired at the time at simulation and used as a reference ultrasound image for localizing tracking target. The ultrasound probe will be placed at the abdominal area to monitor the liver motion. The probe will remain in place during the CT scan. Patient setup and the ultrasound probe location will be recorded so that the same setup could be reproduced during treatment delivery. The ultrasound probe in the CT image will be contoured and radiation beams that directly pass through the ultrasound probe will be avoided.

On each treatment day, 4D ultrasound images will be acquired continuously during beam on time to monitor liver motion. The system will record all relevant images, but will not be used in clinical decision making. These data will be used to evaluate the magnitude of target motion and dosimetry deviation due to the motion. Intra-fraction CBCT images acquired during treatment will be registered with reference CT images. Organ motion registered by ultrasound will be compared to motion recorded by CBCT and the accuracy of the ultrasound system will be evaluated.

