## 7. Study Statistics

a. Analytic plan for primary objectives:

An effective workflow for real time monitoring of abdominal soft-tissue due to respiration using a 4D ultrasound system will be developed through the use of healthy controls. As

described earlier, these controls will provide data for estimating the background reference for abdominal soft tissue. Data collected on controls will be summarized with descriptive statistics. Quantitative analysis of target/organ motion and displacement recorded in 4D real-time ultrasound scan will be carried out to assess both intra- and interfractional variation as described above in the study. This study will help us to ensure delivery of the prescribed target dose while simultaneously minimizing normal tissue damage. We will consider the approach feasible if we are able to successfully complete the procedure and output the associated data for 50% of the study participants. The software will output a motion curve over time. We will calculate the difference between values on the curve and the values from CBCT at the specific time points that CBCT is performed, and summarize the differences using descriptive statistics. A 95% confidence interval for the difference will be reported. These data will be used to evaluate the accuracy of the 4D ultrasound system.

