**c. Sample size justification:**

The goals of this study are to test the feasibility of the approach and subsequently generate data for describing the accuracy of the 4D ultrasound motion monitoring system during pancreas and liver SBRT treatments. The variability of the data obtained is currently unknown, so it is difficult to give preliminary estimates of the precision that specific sample sizes will yield. We plan to enroll 15 healthy controls, 30 pancreatic cancer patients, and 20 hepatic cancer patients for generating the pilot data.

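### Accuracy against CBCT (primary objective c) is to be reported through a confidence interval that, naturally read, measures average bias; no agreement measure is committed to, and repeated differences per patient are not dealt with

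*Combined protocol and SAP*

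**What the plan says.** Section 2 of the combined protocol and SAP lists as primary objective c: "Evaluate accuracy of the 4D ultrasound motion monitoring system compare to CBCT based intra-fraction motion monitoring during pancreas and liver SBRT treatments". Section 4 describes the comparison for both patient arms only in general terms: "Organ motion registered by ultrasound will be compared to motion recorded by CBCT and the accuracy of the ultrasound system will be evaluated".

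The analysis is in section 7a. The pairing is given: "We will calculate the difference between values on the curve and the values from CBCT at the specific time points that CBCT is performed". The plan will then "summarize the differences using descriptive statistics. A 95% confidence interval for the difference will be reported". It does not name the descriptive statistics, the parameter that the interval estimates, the sign convention, or whether the difference is taken per axis or as a 3D magnitude.

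Section 4 has ultrasound acquired on every treatment day in arms 2 and 3, with CBCT taken during treatment, so a patient can contribute several differences. The abstract says of the technique in general: "SBRT delivers high doses of radiation therapy to the tumor over only 1-5 treatments". Section 7a does not mention clustering within patient or whether the two patient arms are pooled.

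Section 7c plans 30 pancreatic and 20 hepatic patients and gives no precision target: "The variability of the data obtained is currently unknown".

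**The concern.** An interval for a mean difference answers one question: is ultrasound off from CBCT on average? Real-time monitoring raises another: how far off may one reading be? A system that errs by several millimetres in both directions can have a mean difference near zero and a narrow interval. Adding patients narrows the interval further but leaves the individual errors unchanged.

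Two things add to this. The difference is incompletely defined, so a signed per-axis mean, an absolute per-axis mean and a 3D magnitude all fit section 7a, and the choice could be made after the data are seen. And if repeated differences from one patient are pooled as independent, the interval is too narrow even as a statement about bias.

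At stake is how useful the pilot result is. Section 7c makes describing accuracy a goal of the study and says the variability is not known. Spread is therefore the quantity that a later study most needs, and no measure of it is promised.

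**Working it through.** The plan states no precision, power or margin for accuracy, so there is no figure of its own to reproduce. The following is an illustration.

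**Inputs from the plan:** n=30 (pancreas) and n=20 (liver), section 7c; 95% level, section 7a; up to 5 fractions, from the abstract's general range.

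**Assumptions:** SD of the difference 1 to 5 mm per axis, since the plan gives none; zero bias; normal errors; one difference per patient in steps 1 to 4.

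**Step 1. Interval for the mean.** Half-width = t(0.975, n−1) × SD/√n. At SD 3 mm:
- n=30: 2.045 × 3/√30 = 1.12 mm
- n=20: 2.093 × 3/√20 = 1.40 mm

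**Step 2. 95% limits of agreement.** Half-width = 1.96 × SD. At SD 3 mm this is 5.88 mm, whatever n is.

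| Assumed SD (mm) | CI of mean, n=30 | CI of mean, n=20 | Limits of agreement | Readings off by more than 3 mm on an axis |
|---|---|---|---|---|
| 1 | ±0.37 | ±0.47 | ±1.96 | 0.3% |
| 2 | ±0.75 | ±0.94 | ±3.92 | 13% |
| 3 | ±1.12 | ±1.40 | ±5.88 | 32% |
| 5 | ±1.87 | ±2.34 | ±9.80 | 55% |

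The last column is 2 × (1 − Φ(3/SD)). The 3 mm there is only a convenient distance, not an acceptance limit.

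**Step 3. Effect of the definition.** At SD 3 mm and n=30, equal SD on three axes:
- signed per axis: expected mean 0, CI ±1.12 mm
- absolute per axis: mean 3 × √(2/π) = 2.39 mm; SD 3 × √(1 − 2/π), so CI ±0.68 mm
- 3D magnitude: mean 6 × √(2/π) = 4.79 mm; SD 3 × √(3 − 8/π), so CI ±0.75 mm

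The absolute and 3D means differ two-fold on the same data. The signed mean is zero by assumption, so no ratio to it is meaningful.

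**Step 4. Precision of the limits.** Half-width of the CI for each limit = t(0.975, n−1) × SD × √(1/n + 1.96²/(2(n−1))). At SD 3 mm:
- n=30: 2.045 × 3 × √(0.0333 + 0.0662) = 1.94 mm
- n=20: 2.093 × 3 × √(0.0500 + 0.1011) = 2.44 mm

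**Step 5. Repeated differences.** Assume one difference at each of 5 fractions, total SD 3 mm, and ICC 0.3 to 0.6. Half-width = t(0.975, n−1) × 3 × √((1 + 4 × ICC)/(5n)). For n=30:
- ICC 0.3: 2.045 × 3 × √(2.2/150) = 0.74 mm
- ICC 0.6: 2.045 × 3 × √(3.4/150) = 0.92 mm
- treated as 150 independent values: 1.976 × 3/√150 = 0.48 mm

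For n=20 the figures are 0.93, 1.16 and 0.60 mm. The limits of agreement stay at ±5.88 mm throughout, because they depend on the total SD.

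**The case against.** The strongest reply is that section 7a promises descriptive statistics as well as the interval. A conventional summary would include an SD or range, and a mean with an SD is enough to form simple limits of agreement. The plan therefore leaves agreement open; it does not rule it out. This stands, and it lowers the severity. It does not remove the point: an SD is not promised, and a pooled SD would not separate within-patient from between-patient error.

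The gap between the interval and the limits can also be called no finding about this trial, since the ratio 1.96√n/t holds for any mean. That too is right. It shows what the stated interval cannot tell the reader, not how this system performs.

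The plan also calls this a pilot, and section 4 keeps the ultrasound data out of clinical decisions. A descriptive analysis is acceptable on that footing, and no test or margin is asked for here.

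A reader might infer that the abstract supplies an accuracy benchmark, because it cites older systems as agreeing with CT "within a small absolute magnitude of difference (about 3 mm), therefore we expect to have good agreement". The documents do not support this. The sentence goes on to concern the reference CT simulation and the reference ultrasound, and the 3 mm is nowhere made a criterion for the motion curve.

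**Conclusion.** The point holds as a cheap improvement of modest severity. For a primary objective, the only inferential output committed to is an interval that, on its natural reading, measures average bias. No agreement measure is named, and the repeated differences per patient are not addressed. At an assumed SD of 3 mm, an interval of ±1.12 mm (n=30) or ±1.40 mm (n=20) would stand beside limits of ±5.88 mm, with about 32% of readings off by more than 3 mm on an axis. With 5 differences per patient and n=30, treating them as independent gives ±0.48 mm, against ±0.74 to 0.92 mm at ICC 0.3 to 0.6. The SD, the ICC and the number of differences per patient are assumptions, so these figures show scale only.

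Two stronger readings should be resisted:
- A reader might infer that the ultrasound-CBCT difference is undefined. It is not: section 7a gives the instruments, the pairing and the time points. Sign, axis or 3D, and the parameter of the interval are what is missing.
- A reader might apply the feasibility rule to each patient arm and conclude that accuracy could rest on 15 and 10 patients. The rule asks the study to "successfully complete the procedure and output the associated data for 50% of the study participants", with no condition by arm, and it sets no standard for accuracy.

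**What to change.** In section 7a:
- Define the difference as signed ultrasound minus CBCT on each axis, plus the 3D error magnitude.
- For each patient arm, report 95% limits of agreement with confidence intervals, by a method that allows for repeated measures within patient.
- Add RMSE or percentiles of absolute error.
- Keep the 95% interval for the mean difference, label it as the estimate of bias, and compute it with within-patient clustering.

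This takes a few lines of text and a little more analysis of data already being collected, with no extra patients or imaging. The cost is in how the result looks. Reported accuracy will seem less favourable than an interval around the mean, and each limit will be imprecise: about ±1.9 mm at n=30 and ±2.4 mm at n=20 if the SD is 3 mm and each patient gives one difference.

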## **3. Background**

SBRT of the abdomen has been limited by the movement of intra-abdominal organs that naturally occurs with respiration and bowel movement. Currently at Johns Hopkins Hospital, breathing motion management is employed using ABC technique for patient treated with pancreas and liver SBRT if the tumor and/or abdominal organs move more than 3 mm during a breathing cycle. While ABC device has been reported to reduce respiratory motion to below 2 mm, small variation of breath-holds may lead to tumor displacement and suboptimal dose delivery. Assessing patient specific tumor/organ motion (both intra- and interfractional) throughout the course of SBRT treatment offers the possibility of ensuring accurate delivery of the prescribed target dose while simultaneously minimizing normal tissue damage. This can be achieved by using Clarity 3D ultrasound system together with ABC device for real-time tracking of the pancreas and liver during SBRT treatment.

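### The accuracy analysis has no zero-motion benchmark and no check that ultrasound follows CBCT, so if motion is small it may not show that the system tracks the organ

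*Combined protocol and SAP*

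**What the plan says.** Section 2 makes accuracy relative to CBCT-based monitoring a primary objective (c). The whole analysis for it is in section 7a: subtract the CBCT value from the motion-curve value at each CBCT time point, then "summarize the differences using descriptive statistics. A 95% confidence interval for the difference will be reported". No acceptable error is set. The one success rule in 7a, 50% of participants completing the procedure with data output, concerns feasibility.

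On the size of the motion, section 3 says "While ABC device has been reported to reduce respiratory motion to below 2 mm" and then, in the same sentence, that "small variation of breath-holds may lead to tumor displacement and suboptimal dose delivery". The Abstract adds that under ABC "tumor and organ motion could only be minimized and not eliminated completely". It also cites ultrasound-to-CT image agreement of about 3 mm from older ultrasound systems. Section 7c states that the variability of the data is unknown.

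Two other planned analyses bear on the point. Section 7a includes a separate quantitative analysis of the motion recorded by ultrasound. Section 4a (Arm 1) re-registers the healthy-volunteer scans in Velocity software to check the built-in registration.

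**The concern.** An ultrasound-minus-CBCT difference can be read as accuracy only against the error made by ignoring motion altogether. When true displacement is small, a device that reports zero also produces small differences, because each difference is then just the CBCT displacement with its sign reversed. A device whose output varies but has nothing to do with the organ can also produce differences of a few millimetres centred on zero.

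The trial could therefore report a mean difference near zero with a narrow interval and describe the system as accurate, without evidence that the curve follows the organ. Objective c would then be reported but not answered.

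**Working it through.** The plan gives no margin, precision or power figure to reproduce.

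**Inputs from the documents.** 30 pancreas and 20 liver patients have CBCT (sections 4 and 7c). The interval is 95% (7a). Respiratory motion under ABC is reported as below 2 mm (section 3).

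**Assumptions, not in the documents.** One difference per patient and axis; two-sided t interval; motion SD sm 0.5 to 3 mm; tracker error SD su 0.5 to 1.5 mm; CBCT error SD sc 0 or 0.5 mm; independent errors with mean zero.

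**Model.** True displacement is m and CBCT reads m + e_c. The SD of ultrasound minus CBCT is:
- following tracker (reads m + e_u): sqrt(su² + sc²)
- zero-output tracker: sqrt(sm² + sc²)
- unrelated tracker (output SD so, independent of m): sqrt(so² + sm² + sc²)

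If m is centred on zero, all three have expected mean difference 0, provided the unrelated output is also centred on zero.

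**Interval half-width**, t × SD/√n, where t/√n is 0.373 at n=30 and 0.468 at n=20. With sm = 1 mm and sc = 0:

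| Tracker | SD (mm) | n=30 (mm) | n=20 (mm) |
|---|---|---|---|
| Zero output | 1.00 | 0.37 | 0.47 |
| Unrelated, so = 1 | √2 = 1.41 | 0.53 | 0.66 |
| Following, su = 0.5 | 0.50 | 0.19 | 0.23 |
| Following, su = 1.0 | 1.00 | 0.37 | 0.47 |
| Following, su = 1.5 | 1.50 | 0.56 | 0.70 |

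The zero-output and unrelated trackers fall inside the range of the following trackers.

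**Simulation** with sc = 0.5 mm (4,000 replicates; 1,000 for tests of SD and correlation), following against zero-output tracker:
- *Mean and interval, motion centred on zero:* the interval excluded 0 in about 5% of replicates for both trackers at n = 20, 30 and 50.
- *SD of the differences, motion uniform on −2 to 2 mm:* for su = 0.5 the SDs are 0.71 (following) and 1.26 mm (zero), and a paired test of the SDs detects this in 74% (n=20), 92% (n=30) and 99% (n=50). For su = 1.0 they are 1.12 and 1.26 mm, detected in 5% to 11%. For su = 1.5 the following tracker looks worse, 1.58 against 1.26 mm.
- *One-directional motion, uniform on 0 to 2 mm:* the zero tracker has a mean near −1 mm and its interval excludes 0 in about 100%.
- *Displacement SD 3 mm:* SDs of 0.71 to 1.59 against about 3.0 mm, detected in 78% to 100%.

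**What the proposed additions would show.** With sc = 0 and sm = 1 mm, the ratio of RMS difference to RMS CBCT displacement is 1 for the zero tracker, 1.41 for the unrelated one, and 0.5, 1.0 and 1.5 for following trackers with su = 0.5, 1.0 and 1.5. With su = 1.5 the ratio is above 1 although the tracker does follow the organ. The slope of ultrasound on CBCT separates these cases: expected value 0 for the zero and unrelated trackers and 1 for the following ones, with SE about su/(sm√n) = 1.5/√30 = 0.27 or 1.5/√20 = 0.34 at su = 1.5.

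In the simulation (sc = 0.5), the chance of detecting a positive correlation for su = 0.5, 1.0 and 1.5 was:

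| Motion SD | n=30 | n=20 |
|---|---|---|
| 1 mm | 1.00, 0.97, 0.83 | 0.99, 0.88, 0.62 |
| 0.5 mm | 0.82, 0.39, 0.23 | 0.65, 0.26, 0.14 |

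CBCT error shrinks the slope by sm²/(sm² + sc²): 1/1.25 = 0.8 for sm = 1, and 0.25/0.50 = 0.5 for sm = 0.5, with sc = 0.5.

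**The case against.** A reader might infer that ABC leaves less than 2 mm of motion, so the planned difference cannot tell a working tracker from a dead one. The documents do not support that. The 2 mm is a reported figure for respiratory motion, and the same sentence warns of further displacement. The Abstract attributes interfraction motion to organ filling, weight change and tumor growth, and no limit is given for that. CBCT is registered to the reference CT, so such shifts may enter the comparison. With larger or one-directional displacement, the planned mean or SD does separate the trackers.

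Nor can the 3 mm figure serve as tracking error or as a tolerance. It is image agreement with older systems. The Abstract says tracking is ultrasound to ultrasound, and 7a sets no 3 mm limit. It would also be wrong to say that a null tracker looks better on every planned summary: the expected mean is the same, and the SD favours a tracker whose error is well below the motion.

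A literally flat output would show in the separate motion summary, and the Velocity check in Arm 1 tests the registration software. These are real safeguards. They do not reach an output that varies plausibly but is unrelated to the organ in patients, and the Velocity check covers only volunteers. The SD helps only if set against the SD of CBCT displacement, a comparison that 7a does not specify.

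Finally, this is a pilot, the system does not guide treatment, and the pairs could be re-analysed later. That limits the consequence, but it does not supply the missing comparison.

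**Conclusion.** The point holds in conditional form. Section 7a has no zero-motion reference and no check that ultrasound follows CBCT; that is plain from the text. If residual displacement is small and centred on zero, the mean difference and its interval may not distinguish a tracker that follows the organ from one whose output is zero or unrelated. The SD of the differences helps only when tracker error is well below the motion SD and the benchmark is shown beside it.

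All SDs here are assumptions, as is one independent difference per patient. Because section 7c says variability is unknown, the analysis should be informative whether motion turns out small or large. This is a worthwhile change to how a primary objective is analysed, not a flaw that invalidates the study.

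**What to change.** In section 7a, per arm and per axis, add two summaries from the same matched pairs:

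1. The RMS ultrasound-minus-CBCT difference beside the RMS CBCT displacement (the error of assuming no motion), with their ratio and a patient-level bootstrap 95% CI. Read a ratio below 1 as improving on the assumption of no motion. Do not use it to decide whether the system carries information: the tracker with su = 1.5 mm above has ratio 1.5, yet weighting its output optimally would cut the error from SD 1.0 to √(2.25/3.25) = 0.83 mm.
2. The slope (or correlation) of ultrasound displacement on CBCT displacement, allowing for repeated measurements per patient, as a descriptive measure. A value near 0 suggests that motion is being missed, subject to the attenuation below.

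The cost is a few lines of text and analysis of data already being collected. Two limits should be stated with the results. CBCT registration error pulls the slope down, to about 0.5 if its SD equals the motion SD. Precision is also modest with 30 and 20 patients, especially if motion SD is near 0.5 mm.
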